3. HUMAN SUBJECTS

3.1 SUBJECT POPULATION

The study population will consist of injured patients at risk of hemorrhage being transported via air medical services from the scene of injury or from referring hospital to a definitive care trauma center participating in the PPOWER pilot trial. Patients will be enrolled in the prehospital setting prior to trauma center arrival with continuation of LTLR-WB resuscitation or standard of care resuscitation during the in-hospital acute resuscitation phase of the study

3.2 INCLUSION CRITERIA

1. Injured patients at the risk of Hemorrhage being transported from scene or referral hospital to a participating PPOWER trial site

AND

2A. Systolic blood pressure \leq 90 mmHg AND tachycardia > 108 bpm at scene, or at outside hospital or during transport.

OR

2B. Systolic blood pressure ≤70 mmHg without tachycardia requirement, at scene or outside hospital or during transport.

3.3 EXCLUSION CRITERIA

- 1. Documented age: Age ≥90 or <18 years of age
- 2. Inability to obtain intravenous or interosseous access
- 3. Isolated fall from standing injury mechanism
- 4. Known prisoner or known pregnancy
- 5. Traumatic arrest with > 5 minutes of CPR without return of vital signs
- 6. Brain matter exposed or penetrating brain injury (GSW)
- 7. Isolated drowning or hanging victims
- 8. Isolated burns without evidence of traumatic injury
- 9. Referral Hospital In-patient admission
- 10. Objection to study voiced by subject or family member at scene
- 11. Wearing PPOWER opt-out bracelet

Inclusion and exclusion criteria will be assessed based on available information at the time of enrollment. Although all reasonable efforts will be made by the air medical crew to either directly witness or obtain documentation of eligibility criteria, due to the nature of the emergency pre-hospital setting, there may be occasions where the air medical crew must rely on verbal report of inclusion criteria, including qualifying vitals, from the referring hospital or ground crew. In these instances, if, after subsequent review of outside hospital and/or ground crew documentation, it is determined that the subject did not meet inclusion criteria and/or met exclusion criteria, the subject will remain enrolled in the study based on the intention-to-treat principle.

In the event that a verbal report must be used in lieu of physical documentation or directly witnessing the qualifying vitals, documentation of the verbal report will serve as the source documentation for determining eligibility. Verbal reports will be documented in the air medical record and will detail the information reported and by whom.

4. IRB APPROVAL AND FDA AMENDMENTS

The Investigator will obtain, from the University of Pittsburgh Institutional Review Board (IRB), prospective approval of the clinical protocol and corresponding informed consent form(s); modifications to the clinical protocol and corresponding informed consent forms, and advertisements (i.e., directed at potential research subjects) for study recruitment.

The only circumstance in which a deviation from the current IRB-approved clinical protocol/consent form(s) may be initiated in the absence of prospective IRB approval is to eliminate an apparent immediate hazard to the research subject(s). In such circumstances, the Investigator will promptly notify the University of Pittsburgh IRB of the deviation. The Investigator should also notify the sponsor of this event.

The University of Pittsburgh IRB operates in compliance with FDA regulations at 21 CFR Parts 50 and 21 CFR 56, and in conformance with applicable International Conference on Harmonization (ICH) Guidelines on Good Clinical Practice (CGP).

In the event that the University of Pittsburgh IRB requires, as a condition of approval, substantial changes to a clinical protocol submitted under an FDA-accepted IND application, or in the event of the Investigator's decision to modify the previously accepted clinical protocol, a Protocol Amendment will be submitted to the IND file for FDA review and comment prospective of implementation of the changes, as required. Changes that require prospective submission include:

• Any significant change in the design of the protocol (such as the addition or deletion of a control group).

The addition of a new test or procedure that is intended to improve monitoring for, or reduce the risk of, a side effect or adverse event; or the dropping of a test intended to monitor the safety of the investigational drug.

5. RECRUITMENT AND INFORMED CONSENT PROCEDURES

5.1 RECRUITMENT METHODS:

Subjects will be enrolled under "Exception from Informed Consent for emergency situations."

Subjects will be identified by prehospital air medical personnel at the scene, in transit or when being picked up from a referring facility. Subjects not enrolled by prehospital personnel but who meet all inclusion and no exclusion criteria may be identified and enrolled by research personnel after arrival to the ED and will be analyzed based on the arm assignment from which they originated per the intention to treat analytic plan.

In cases where the subject is incapacitated and unable to provide direct consent and an appropriate LAR is not present in the hospital, the consent will be obtained by phone/fax or electronically. The study will be discussed with the LAR over the telephone. If the LAR agrees, the consent form (ICF) will be sent electronically (email, fax, DocuSign, etc.) to the LAR. The investigator will go over the ICF with the Legally Authorized Representative. If the LAR agrees to participate in the research, the LAR will sign the ICF and send back to the Principal investigator electronically. An electronic picture of the signed signature page.forwarded to the consenting Investigator, will be accepted. The consent form may also be sent to the LAR via DocuSign, where the document can be reviewed in detail and digitally signed.

We will also send a postage paid envelope to the LAR for returning of the original complete signed informed consent whenever consent is obtained via email or fax.

If initial consent is obtained via LAR, the study team will routinely monitor the subject for capacity to consent while still admitted to the hospital. If it is determined by the Investigator, in conjunction with the assessment of the clinical team, that the subject has regained capacity, the Investigator will conduct the inform consent discussion and attempt to obtain continuing consent.

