2.2 DETAILED DESCRIPTION OF STUDY DESIGN

Study Population: The study population will consist of injured patients at risk of hemorrhage being transported via air medical services from the scene of injury or from referring hospital to a definitive care trauma center participating in the PPOWER pilot trial. Patients will be enrolled in the prehospital setting prior to trauma center arrival with continuation of LTLR-WB resuscitation or standard of care resuscitation during the in-hospital acute resuscitation phase of the study.

Study Population Rationale: The most appropriate patient population who would benefit most from early, prehospital initiation of LTLR-WB are those with potentially survivable injuries, at risk of the detrimental complications attributable to hemorrhagic shock, using criteria which can be widely generalizable in the real-world prehospital setting. In the prehospital phase of treatment, complete characterization of injuries and injury severity is not possible. We have chosen inclusion and exclusion criteria based upon preliminary data obtained from the PAMPer study, a recently closed pragmatic prehospital trial at the University of Pittsburgh.⁴⁰ The incidence of arrival shock (87%) and coagulopathy (41%), the need for large volume transfusion (36%) and the development of multiple organ failure (25%) and overall mortality (30%) utilizing the proposed inclusion and exclusion criteria, with appropriate modifications, will provide the most appropriate patient population to demonstrate the benefits of LTLR-WB resuscitation.

Group O whole blood represents a precious blood banking resource. There exists an even further limited supply of Rh negative, group O whole blood (6.6% of blood supply overall). Due to this supply limitation, the only feasible and sustainable approach for whole blood resuscitation is to utilize Rh positive group O whole blood, which is significantly more common (37.4% of blood supply overall).

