2.6 RANDOMIZATION

Procedures Assuring Adherence to Randomized Assignment: Enrollment will occur in the prehospital phase of the trial and LTLR-WB or prehospital standard of care will be provided based upon randomization assignment. Prehospital providers will designate the patient as enrolled and notify receiving staff of the treatment arm. Research staff will be present upon arrival and will communicate directly with blood banking staff/anesthesia and the trauma team regarding the randomization arm of the patient. Once in-hospital, LTLR-WB randomized patients may receive LTLR-WB transfusion as indicated during this acute resuscitation phase of in-hospital care up to 6 units in-hospital and 8 units of LTLR-WB total.

Randomization and Blinding: A single stage cluster randomization scheme will be utilized. Designated air medical bases at the University of Pittsburgh will be block randomized and assigned to the LTLR-WB arm or Standard of Care (control) arm for 1 month time intervals. The cluster design will be at the level of the helicopter base. The block scheme will vary randomly between 2 and 4 month block sizes over the period of enrollment for the trial. Randomization assignments will be determined prior to the start of the bases enrollment following the above single stage cluster design using standard computerized randomization software. Communication with the blood bank transportation services and each respective air base will occur and an annual schedule of randomization assignment will be distributed to each study air base. This specific randomization scheme is required due to the limited supply of O+ LTLR-WB and also due to the logistics and delivery of the intervention in the prehospital setting. The

proposed pilot trial will be an open label trial as blood product transfusion requires appropriate documentation and essential look back procedures.

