2.9 STATISTICAL ANALYSIS

The overarching goals for the pilot trial are to evaluate safety, efficacy and feasibility of a LTLR-WB prehospital through in-hospital protocol to plan for the successful execution of a large, multicenter clinical trial. All analyses will be performed based on the intent-to-treat principle for the prehospital randomization and analyses will include all enrolled patients grouped by randomization assignment. This pilot study will guide the calculation needed for the large, multicenter clinical trial and will provide estimation for intra-cluster correlation coefficient and sample size variation across clusters. We will report 95% confidence intervals for all measurements

Safety and Efficacy Analysis: 28-day mortality is the primary safety and efficacy outcome and will be compared across randomized groups. Utilizing intention to treat principles we will compare the LTLR-WB and Standard of Care arms using a pooled Z test for comparing two independent proportions. We will additionally perform survival analysis for all mortality outcomes including 3hr, 6hr, 24hr, and 28day time points across the two arms of the study testing the differences using log rank test.

Eligibility, Enrollment, and Subject Accrual Anlaysis: The feasibility of enrollment will be evaluated by determining 1) the number of patients that meet the eligibility criteria for the trial; 2) the proportion of eligible patients that can be randomized and 3) the proportion of eligible patients who are enrolled in the trial. These proportions will be estimated directly as the observed ratio of numbers of patients, and 95% confidence intervals will be calculated to understand the likely range of values for a larger study with a comparable research protocol. The reasons why patients are not enrolled including frequencies of individual exclusions and the proportion of patients declining participation or not able to be randomized will be described. Rate of subjects' accrual per month with 95% C.I. will be calculated.

Adherence and Minimization of Bias: Adherence rates for each treatment arm of the protocol will be ascertained as the proportion of enrolled patients who adhere to the intervention (LTLR-WB vs. standard care) as assigned. Estimated proportions and 95% confidence intervals will be created. The trial has been designed to negate intervention arm crossover and maximize follow-up completion.

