6.5.2 Protection Against Potential Risks of Experimental Intervention

MACRO research coordinators for the pilot trial will document and verify all trauma arrivals via air medical transport for PPOWER enrollment. Those patients who met inclusion and exclusion criteria during air medical transport that were enrolled will be verified and those patients will undergo initial laboratory and blood sampling within the first hour of arrival. All requirements for notification for exception from informed consent for emergency research and Title 21, Code of Federal Regulations, Section 50.24 (21 CFR 50.24) will be explicitly followed (Appendix 4).

Training and Participating Site Coordination: As the clinical coordinating center for the proposed pilot trial the University of Pittsburgh will be responsible for all research coordinator training, prehospital provider training and sample collection and storage. Research coordinators, prehospital providers and associated staff will be trained during the months prior to the trial start date regarding the scientific basis for the study, specific inclusion and exclusion criteria, sample collection and processing, prehospital procedures and SOPs, and rapid TEG performance. Trial enrollment and maintenance of data integrity will be assessed monthly using the web-based data platform. Trial screening, enrollment and data completeness and accuracy will be accessed at regular intervals via random patient audit.

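### Section 5.1 makes ED enrolment of missed patients optional with nothing concealing the arm, and 2.8 gives conflicting mortality time origins that leave deaths before arrival without a counting rule

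*Combined protocol and SAP*

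**What the plan says.** **Enrolment.** Section 2.2 states: "Patients will be enrolled in the prehospital setting prior to trauma center arrival". Section 3.1 repeats the sentence and 2.6 agrees. Section 5.1 adds a second route: eligible patients whom the crew did not enrol "may be identified and enrolled by research personnel after arrival to the ED", analysed in the arm they came from. It sets no time limit and no duty to enrol every such patient.

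**Knowledge of the arm.** The trial is open label (2.1, 2.6). Bases are assigned by month, and an annual schedule goes to each base (2.6). At arrival, research staff "will communicate directly with blood banking staff/anesthesia and the trauma team regarding the randomization arm of the patient".

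**Eligibility and analysis set.** Under 3.2 the qualifying vital signs are values "at scene, or at outside hospital or during transport". Section 3.3 says: "Inclusion and exclusion criteria will be assessed based on available information at the time of enrollment". Section 2.9 says that "analyses will include all enrolled patients grouped by randomization assignment".

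**Safeguards.** In 6.5.2, coordinators "will document and verify all trauma arrivals via air medical transport". Section 2.9 will describe "The reasons why patients are not enrolled including frequencies of individual exclusions". Section 6.4.2 and Appendix 8 Table 3 tabulate eligible patients not enrolled, the latter by arm.

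**Mortality timing.** The list of secondary outcomes in 2.8, which includes mortality, opens with a 28-day period counted from randomization. The mortality item in that list counts 3, 6 and 24 hours from arrival. The outcome definitions count 6 and 24 hours from the time of admission, and in-hospital and 28-day mortality from the date of admission. The primary outcome is all-cause 28-day mortality in 2.8 and 2.9. In the 6.4.2 analysis plan, its interim analysis and Appendix 8 Table 2, the primary comparison is in-hospital mortality.

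**The concern.** An optional enrolment step, taken after arrival by someone from whom the arm is not concealed, lets the denominator depend on the arm and on how the patient is doing. Analysis by originating arm settles which column a late enrolment goes in. It does not settle who enters the table.

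The timing issue is distinct. Assignment and treatment begin in the air, and deaths before arrival are among the early deaths that a prehospital intervention aims to prevent. Whether such a death counts, and from when it is timed, should not depend on which of two stated primary outcomes or which of several clocks an analyst picks up.

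**Working it through.** **1. The plan's own figure.** Inputs from 2.9: 56 per arm, 33% v 11%, two-sided alpha 0.05, bounds 2.96259 and 1.96857. Pooled rate = (0.33 + 0.11)/2 = 0.22. Drift = 0.22 / √(0.22 × 0.78 × 2/56) = 2.810 (stated 2.81024). The two-look power is 0.801 (stated 0.800921). It reproduces.

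The illustrations below need a baseline from the test itself. Binomial simulation of the pooled Z test at 28 and then 56 per arm (1,000,000 runs) gives power 0.828, and null rejection 0.053 with 33% in both arms. **Every count from here on is assumed; the documents give none.**

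**2. ED additions in one arm, no true effect.** If m of the 56 are ED-added with mortality q, arm rate = [(56 − m) × 0.33 + m × q]/56. For m = 4 and q = 0.20: (17.16 + 0.80)/56 = 32.1%.

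| q | Arm rate, m = 2/4/6 | Null rejection (within about 0.1 point) |
|---|---|---|
| 0% | 31.8/30.6/29.5% | 5.3/5.9/6.8% |
| 20% | 32.5/32.1/31.6% | 5.2/5.3/5.4% |
| 50% | 33.6/34.2/34.8% | 5.3/5.4/5.7% |

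**3. Opposed selection in both arms.** This is a harsher assumption. Exact enumeration at the final look only has a baseline of 5.2%.
- 10% of each arm ED-added, mortality 50% (control) v 16% (whole blood): 0.9 × 0.33 + 0.1 × 0.50 = 34.7%, against 0.9 × 0.33 + 0.1 × 0.16 = 31.3%. The gap is 3.4 points and rejection 6.9%.
- 20% of each arm, 60% v 10%: 38.4% v 28.4%. The gap is 10.0 points and rejection 20.5%.

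**4. Would the reported counts reveal it?** Suppose M patients are missed in each arm, all are enrolled in one arm and each has a 50% chance of enrolment in the other. A two-sided Fisher test at 0.05 flags the imbalance 6% of the time for M = 4, 11% for M = 6 and 62% for M = 10.

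**5. Deaths before arrival.**

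| Outcome used | Pre-arrival death of an enrolled patient |
|---|---|
| All-cause 28-day mortality, intention to treat (2.8, 2.9) | Counts; power unaffected |
| In-hospital mortality (6.4.2, interim, Table 2) | Not naturally an in-hospital death; no rule stated |
| 3, 6, 24 h and log-rank from arrival or admission (2.8) | No time zero |
| Period from randomization (2.8) | Has a time zero, but conflicts with the row above |

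If, and only if, in-hospital mortality is used and exactly k pre-arrival deaths go uncounted with the denominator kept at 56:

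| k = 1/2/3 lost from | Power (base 82.8%) | Null rejection (base 5.3%) |
|---|---|---|
| Control only | 77/70/62% | 5.9/7.6/10.4% |
| Each arm | 85/86/88% | 5.6/6.0/6.5% |
| Whole blood only | 89/93/96% | as for control only, by symmetry |

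A single case shows the sensitivity. 18/56 v 9/56 gives Z = 1.988, beyond 1.969. With one control death uncounted, Z is 1.790 for 17/56 or 1.845 for 17/55, and both fall inside the bound.

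**The case against.** **The discretion in 5.1 is narrow.** A missed patient must meet every criterion, the qualifying vital signs are pre-arrival values, the arm is fixed by origin, and arrivals are logged. The route may also recover patients whom an arm-aware crew passed over. All of this stands, and it is why the effect is probably small. It does not turn an option into a rule.

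**A reader might infer from 2.6 that ED research staff are told the arm of each missed patient.** The documents do not support that. The relay described there concerns patients already designated as enrolled. The support for saying that the arm can be known is the open-label design and the advance schedule. That schedule is distributed to the bases, so actual knowledge in the ED is an inference.

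**A reader might also infer that the plan drops deaths before arrival, or that its power is wrong.** Neither follows. No passage excludes such patients. Section 2.9 keeps all enrolled patients in the analysis, all-cause 28-day mortality counts the death, and 2.8 itself offers an origin at randomization. The power and type I figures in step 5 also score a known death as a survivor, which no passage prescribes. If 28-day mortality is confirmed as primary throughout, those figures fall away. The time origin for the early time points and the log-rank tests would still need settling.

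The flow chart is not reproduced in the text available, so a rule given only there could not be checked.

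**Conclusion.** Both parts hold as gaps in the rules; neither is evidence of bias that has occurred.

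**Enrolment.** The sections conflict on when enrolment happens, and the optional ED route allows selection that the safeguards can reveal but not prevent. With small one-arm additions the effect is small: null rejection is 5.2% to 6.8% over the assumed range, against 5.3%. It becomes material only if ED additions are a sizeable share of both arms and are selected in opposite directions. With few missed patients, the reported counts would seldom expose it.

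**Mortality timing.** Section 2.8 has conflicting origins, and a death before arrival has no stated place in the early, log-rank or in-hospital analyses. The stated 80% power is sound for all-cause 28-day mortality. The figures for uncounted deaths are illustrations that apply only under in-hospital mortality.

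The changes should be made because they are cheap and settle who is counted before the data are seen. Confidence is medium, since size and direction are unknown.

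**What to change.** - **5.1:** replace the option with a duty to enrol every eligible missed patient found in the 6.5.2 arrival log. Judge eligibility only on prehospital or referral-hospital data and, as far as practicable, before the base-month assignment is looked up. Complete separation cannot be assured in an open-label trial. Align 2.2, 2.6 and 3.1.
- **2.8:** use one origin, prehospital enrolment, for all mortality clocks. ED-enrolled patients should join the risk set of the time-to-event analyses only at ED enrolment (delayed entry), so that no guaranteed-survival time is credited to them.
- **2.8, 2.9, 6.4.2 and Appendix 8:** state that the death of any enrolled patient before arrival counts in the assigned arm in every mortality comparison, including the interim. Reconcile the named primary outcome.
- **Reporting:** show ED enrolments by arm, and add an analysis restricted to prehospital-enrolled patients. Present it as one sensitivity check only, because crews also know the arm.

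The cost is wording, some extra record review, a recorded enrolment time for each patient and one added analysis. One limit remains: ED-enrolled patients have survived to arrival by definition. Delayed entry handles this in the time-to-event analyses but not in simple proportions.

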5.2 INFORMED CONSENT PROCEDURES

We anticipate that the pilot study will be conducted under the auspices and requirements of exception from informed consent for planned emergency research with regulatory oversight by the Food and Drug Administration (FDA) and Title 21, Code of Federal Regulations, Section 50.24 (21 CFR 50.24). This entails obtainment of an Investigational New Drug (IND) approval from the FDA, local IRB approval, community consultation, public notification, as well as notification of patients or their legally-authorized representative as soon as feasible after enrollment. Per regulation, we will attempt to obtain prospective informed consent from the subject or an appropriate LAR whenever feasible). However, we anticipate that prospective informed consent will not be feasible for the majority, if not all, of subjects enrolled. The patient and/or family member or LAR will be informed at the earliest feasible opportunity of the subject's inclusion in the clinical trial, and the details of the trial. If obtaining informed consent is not feasible and a legally authorized representative is not reasonably available, the investigator has committed, if feasible, to attempting to contact the subject's family member who is not a legally authorized representative, and asking whether he or she objects to the subject's participation in the clinical investigation. The investigator will summarize efforts made to contact family members and make this information available to the IRB at the time of continuing review if requested. The investigators will utilize available information and resources, such as social workers or social work notes, to try to locate the patient's legally authorized representative. If that search is unsuccessful, a notification letter will be sent to the subject's authorized representative explaining the study and providing contact information for answering questions. The letter will be sent via registered mail or by UPS and documentation of the addressee and date of mailing will be kept. If the subject becomes competent during the study period then he/she will be approached by a study Investigator for notification of enrollment and a similar provision of an opportunity to opt out from ongoing participation at the earliest opportunity. At any circumstance a subject or their legally authorized representative will have an opportunity to opt out of ongoing participation without penalty or loss of benefits. If the subject dies before consenting, a letter notification will be sent to the subject's family member to inform them that the subject was enrolled in this study.

Community consultation as outlined by the local IRB will be undertaken prior to IRB approval. Feedback from the community will be obtained by research personnel regarding any concerns they may have about potential enrollment. Bracelets will be made available that could be worn by members of the community who do not want to participate. Public notification and community consultation will be performed as directed by the local IRB and may include such methods as using random digit dialing telephone surveys of the proposed study community, targeted small group meetings, newspaper adds, bus add, social media, or consultation with community leaders. Due to ongoing participation and coordination of multiple large multicenter studies of this type, our institution has significant experience with community consultation and notification practices. Our community consultation plan is attached as an appendix (Appendix 3)

The following document describes the **PPOWER study** plan for Waiver of Consent for Planned Emergency Research in compliance with 21 CFR 50.24. We are requesting this waiver because these human subjects are in a life-threatening situation, current available treatment is unsatisfactory, and it is necessary to determine the safety and effectiveness of whole blood transfusion in the prehospital setting. Obtaining informed consent is not feasible because the

subjects will be unable to provide consent due to their medical condition and the intervention will need to be administered before consent from a legally authorized representative is feasible. Public disclosure to the communities in which the clinical investigation will be conducted and from which the subjects will be drawn, prior to initiation of the clinical investigation, of plans for the investigation and its risks and expected benefits.

